7.3.1.2. Measures of incidence (*P. falciparum* infection and clinical malaria)

First or only episode

Vaccine efficacy against first or only episode of incident *P. falciparum* infection or clinical malaria will be analyzed by Cox regression stratified by study site, and overall. The 95% CI and p-values of the vaccine efficacy estimates (1- Hazard Ratio) will be calculated from this model. Cumulative incidence graphs will be produced.

• All episodes

Vaccine efficacy against all episodes of clinical malaria will be analyzed by negative binomial regression allowing for interdependence between episodes within the same subject (non-linear mixed model with over dispersion parameter estimated from the random effect). The 95% CI and p-values of the vaccine efficacy estimates (1- Incidence Rate Ratio) will be calculated from this model. In case models do not converge or showed poor fit, alternative negative binomial models without random effects will be applied. fourteen days following an episode meeting the case definition under evaluation will be subtracted from the follow-up time. The distribution of the total number of events per subject will be tabulated by group. Results per site and overall (adjusted for site as a fixed effect) will be summarized in tables and forest plots.

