Epoch 002	open
Epoch 003	open
Epoch 004	open

- **Sampling schedule:**

- Blood samples for immunogenicity will be taken in all subjects at timepoints described in [Table 5](#). For the evaluation of anti-CS and anti-HBs responses, a subset of 50 subjects (25 subjects per site) in each group (immunogenicity subset, see Section 5) will be tested at specified timepoints (see [Table 5](#) and Section 6.7.4.1). [\[CC1\]](#)
[REDACTED]
- In addition to the blood samples listed in [Table 5](#), a small amount of blood (for blood smear and filter paper) will be taken every month from Day 0 until Month 20, and thereafter every three months until Month 50 **for blood smear and until Month 32 for filter paper** in all subjects for the evaluation of *P. falciparum* infections (see Section 6.7.4.2).

Amended 14 November 2019

- Blood samples for the evaluation of biochemistry and hematology parameters will be taken in a sub-cohort consisting of the first 50 subjects (25 subjects per site) enrolled in each group (reactogenicity sub-cohort, see Section 5). Biochemistry (ALT, creatinine) and hematology (hemoglobin, WBC, platelets) parameters will be assessed before Dose 3, seven days post-Dose 3 and 30 days post-Dose 3 (see [Table 5](#) and Section 6.7.4.3).

Table 5 Blood sampling timepoints

		Visit 1	Visit 2	Visit 4	Visit 5	Visit 6	Visit 10	Visit 11	Visit 12	Visit 18	Visit 19	Visit 24	Visit 25	Visit 27	Visit 28	Visit 30	Visit 31	Visit 33	Visit 34	Visit 38
Study group	Type of blood sampling	Scr	D0	M2	M2 + 7d	M3	M7	M7 + 7d	M8	M14	M15	M20	M21	M26	M27	M32	M33	M38	M39	M50
R012-20	Safety	x*		x**	x**	x**														
	Immunogenicity§		x	x		x						x	x							x
R012-14-mD	Safety	x*		x**	x**	x**														
	Immunogenicity§		x	x		x				x	x			x	x		x	x	x	x
Fx012-14-mFxD	Safety	x*		x**	x**	x**														
	Immunogenicity§		x	x		x				x	x			x	x		x	x	x	x
Fx017-mFxD	Safety	x*					x**	x**	x**											
	Immunogenicity§		x	x		x		x		x	x		x	x		x	x		x	
Control	Safety	x*		x**	x**	x**														
	Immunogenicity§		x	x		x						x								x

* At screening, hemoglobin will be assessed in all subjects screened.

** Blood samples for hematology and biochemistry will be taken in a sub-cohort consisting of the first 50 subjects enrolled in each group.

§ Blood samples for immunogenicity will be taken in all subjects enrolled.

Scr: Screening

M: Month

D: Day

- **Efficacy surveillance:**

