 - The occurrence of solicited local and general AEs in the first 50 subjects enrolled in each group within four days (day of vaccination and three subsequent days) after Dose 3 of study vaccine (all groups including controls), after Dose 4 (groups R012-20, R012-14-mD, Fx012-14-mFxD and Fx017-mFxD), after Dose 5 (groups R012-14-mD, Fx012-14-mFxD and Fx017-mFxD) and after Dose 6 (groups R012-14-mD and Fx012-14-mFxD).

11.3. **Tertiary endpoints**

- **Immunogenicity**
 - Anti-CS antibody avidity at specified timepoints.

11.4. **Determination of sample size**

For the primary endpoint, demonstrating incremental vaccine efficacy against clinical malaria of a fractional dose schedule over the standard schedule, the study has at least 90% power to show a significant incremental vaccine efficacy (lower limit of 95% CI above 0), assuming 250 evaluable subjects per group and an incidence of at least 0.5 episodes/person year at risk (pyr) in the Control group, 0.29 episodes/pyr in the standard schedule groups and 0.16 episodes/pyr in the fractional dose schedule. This corresponds to an incremental efficacy (1-Hazard Rate) of 50% of the fractional dose schedule over the standard schedule. The primary endpoint compares the R012-20+R012-14-mD groups versus the Fx012-14-mFxD group (2:1). For secondary endpoints evaluating efficacy against *P. falciparum* infections, it is anticipated that incidence of infection in the study will be higher than incidence of clinical malaria resulting in adequate power.

In this study the reactogenicity (solicited local and general AEs) and the biochemistry and hematology parameters will be evaluated in a sub-cohort consisting of the first 50 subjects enrolled in each group (total 250 subjects). The anti-CS and anti-HBs immune responses will be tested in a subset consisting of the first 50 subjects enrolled in each group (total 250 subjects); see the [glossary of terms](#) for the definitions of subset and sub-cohort.

Assuming a post-vaccination anti-CS GMC of approximately 50 IU/ml for the fractional dose schedules and a log SD of 0.5 the precision obtained by 95% CIs of the GMC with a sample size of 50 subjects per group is (36.3-68.8).

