7.1. Demography

7.1.1. Analysis of demographics/baseline characteristics planned in the protocol

A study flow diagram (consort) will be generated to present the number of subjects screened, randomized, receiving doses and included in the PPS analyses.

Demographic characteristics (age and gender) and the baseline hemoglobin level will be tabulated per study group overall, and by site, for each cohort (ES, PPS cohort for efficacy and PPS cohort for immunogenicity).

The mean age at first vaccination (in months) (plus range and standard deviation [SD]) of the vaccinated subjects as a whole, and per group, will be calculated.

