8. ANALYSIS INTERPRETATION

Vaccine efficacy estimates with a lower limit of the 95% CI above 0 are to be considered statistically significant.

If the standard schedule of 3 full doses at month 0, 1 and 2 is not statistically significantly superior to the control group in terms of efficacy, the other secondary objectives should be interpreted in the light of this finding.

In order to control alpha not only for the primary objective but also for the secondary objective of incremental efficacy over the 12-month period post-dose 3 of a schedule with a fractional dose at month 7 versus 3 full doses, a sequential approach will be implemented (hierarchical testing). The endpoints will be analyzed sequentially and any conclusion on the secondary endpoint will be conditional to reaching the primary endpoint. All other secondary endpoints should be interpreted descriptively.

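### The primary Cox model adjusts for site only; naming age, the Day-0 slide and screening haemoglobin in it would be a cheap gain in precision, not a repair of the stated 90% power

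*SAP*

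**What the plan says.** SAP 7.3.1.2 states that efficacy against a first or only episode "will be analyzed by Cox regression stratified by study site, and overall". Protocol 11.7.2 gives the same site-stratified Cox model. Neither names a child-level covariate for the primary comparison. SAP 11.1.4.4 requires every covariate in such a model to be set out in the body of the SAP, so as written there are none.

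The candidate covariates are collected. SAP 7.1.1: "Demographic characteristics (age and gender) and the baseline hemoglobin level will be tabulated per study group overall, and by site". Haemoglobin is measured in everyone screened. Under Protocol 3, blood for smear and filter paper "will be taken every month from Day 0 until Month 20" in all subjects. The SAP gives age and haemoglobin only a descriptive role. It uses slides for prevalence and for eligibility in the incident-infection analyses.

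The SAP does adjust elsewhere. For comparisons over unequal calendar time, 7.3.1.1 treats site and the control group's monthly parasitaemia prevalence as prognostic and puts both in the model.

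The power statement is in Protocol 11.4. It claims at least 90% power, "assuming 250 evaluable subjects per group and an incidence of at least 0.5 episodes/person year at risk (pyr) in the Control group", with "0.29 episodes/pyr in the standard schedule groups and 0.16 episodes/pyr in the fractional dose schedule" and 2:1 allocation. It mentions no covariate adjustment.

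**The concern.** In a Cox model, a prognostic baseline variable that is left out costs power even when allocation is balanced, because the unadjusted hazard ratio lies closer to 1 than the hazard ratio among children of equal risk. Age, parasitaemia at enrolment and haemoglobin could plausibly predict time to first clinical malaria, and all three are already in the database.

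The primary result also carries more than itself. SAP 8 makes any conclusion on the Month 7 fractional schedule versus three full doses over 12 months depend on meeting the primary endpoint first. Added power on the primary comparison therefore also helps that second objective to be reached.

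**Working it through.** **Inputs.** From Protocol 11.4: 250 evaluable children per group, hence 250 fractional versus 500 pooled standard, at 0.16 and 0.29 episodes/pyr. From Protocol 11.1: Month 2.5 to Month 14, i.e. 11.5/12 = 0.958 year. From SAP 8: success if the lower 95% limit of incremental efficacy is above 0, i.e. two-sided 0.05. Not in the documents: the prognostic strength of the three covariates. It is assumed here as the SD of their combined contribution to the log hazard, over 0.3 to 1.0. A child one SD above average then has exp(0.3) = 1.35 to exp(1.0) = 2.72 times the average hazard.

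**Step 1: reproduce the stated power with no covariate.**
- Hazard ratio: 0.16/0.29 = 0.552; log hazard ratio −0.595.
- First-event probabilities: 1 − exp(−0.16 × 0.958) = 0.142 and 1 − exp(−0.29 × 0.958) = 0.243.
- Expected events: 250 × 0.142 = 35.5 and 500 × 0.243 = 121.3; total 156.9 (from unrounded values).
- Schoenfeld: z = √(156.9 × 1/3 × 2/3) × 0.595 − 1.96 = 1.55, power 94.0%. Events needed for 90%: (1.96 + 1.28)² / (2/9 × 0.595²) = 134.
- Wald on expected events: SE = √(1/35.5 + 1/121.3) = 0.191; z = 0.595/0.191 − 1.96 = 1.16, power 87.7%.
- Other approximations: two proportions 90.7%, Poisson rates 90.3%, generalised Freedman 87.5%.
- Direct simulation of the site-stratified Cox model, 4,000 trials: 90.6%.

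The formulas spread on both sides of 90%. The simulation of the planned model lands on it. Protocol 11.4 adds: "This corresponds to an incremental efficacy (1-Hazard Rate) of 50% of the fractional dose schedule over the standard schedule". The stated rates give 1 − 0.552 = 44.8%, so the check uses the less favourable of the two effects; a hazard ratio of 0.50 simulates to 96.4%.

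**Step 2: add a baseline score, holding the group rates at 0.29 and 0.16.** Each child gets a standard normal score multiplied by the assumed SD. Baseline hazards are set so that each group's first-event probability over 11.5 months stays as in Step 1. Each of 4,000 simulated trials per setting is analysed twice, without and with the score (Monte Carlo SE about 0.5 point).

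| Assumed log-hazard SD | Power, site only | Power, site + score | Gain (points) | HR among children of equal score |
|---|---|---|---|---|
| 0.3 | 90.3% | 91.2% | 0.9 | 0.549 |
| 0.5 | 90.5% | 91.3% | 0.8 | 0.542 |
| 0.7 | 90.9% | 93.8% | 2.9 | 0.532 |
| 1.0 | 90.8% | 96.2% | 5.4 | 0.510 |

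Power without the covariates stays at 90 to 91% throughout. Adjustment adds to it at every strength.

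**The case against.** The case for leaving the model alone is good, and most of it stands. Under randomisation the site-stratified analysis is valid, and site matches the factor used in the minimisation. The primary groups share calendar time, so the seasonal adjustment in SAP 7.3.1.1 is not needed here. Eligibility narrows the covariates: age is limited to 5–17 months, and haemoglobin below 8 g/dl and moderate or severe malnutrition are excluded. The Day-0 slide precedes the start of follow-up by about ten weeks. The lower half of the assumed range, with a gain of about 1 point, may therefore be the realistic one. Adjustment also changes the estimand to a conditional hazard ratio. And because SAP 11.1.1.2 does not replace missing laboratory results, children without a readable Day-0 slide could fall out of the model. These points limit the size of the gain and dictate what the fix must contain. They do not remove the gain.

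On the other side, a reader might infer that the trial falls short of 90% unless it adjusts. That picture arises if 0.29 and 0.16 are taken as rates for a child of average risk and the per-child hazard ratio is fixed. Unadjusted power then falls from 90.2% at SD 0.3 to 78.8% at SD 1.0. But that simulates a different trial. At SD 1.0 the expected events drop from 156.9 to 137.0, and the population first-event rates become 0.245 and 0.144, a ratio of 0.588. Protocol 11.4 gives its rates for the groups and expresses them as a hazard comparison for the primary endpoint, which is analysed as first or only episode. Even on that reading, the adjusted model reaches only 86.9% at SD 1.0. Keeping the standard group at 0.29 and fixing only the per-child ratio at 0.552 gives a milder fall, from 90.5% to 83.4%, but again with a weaker population effect than the one planned.

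Nor is the movement of the unadjusted hazard ratio towards 1 a bias. The marginal and conditional hazard ratios are different quantities, because the hazard ratio is non-collapsible.

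**Conclusion.** The point holds as a missed efficiency gain. The primary model leaves unused three baseline variables that every child has recorded. Pre-specifying them would raise power by about 1 point if they are weak to moderate (SD 0.3–0.5) and by about 3 to 5 points if they are strong (SD 0.7–1.0). The power statement in Protocol 11.4 is not in error on this account: it was set without covariates and reproduces without them.

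The figures assume the stated group rates, full follow-up of 250 and 500 children, proportional hazards within score, and a normally distributed score that the model captures completely. Three real covariates entered linearly or as categories may capture less, so the adjusted column is the favourable end for each SD. The strength of the covariates is an assumption throughout.

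This is a cheap improvement, not a required correction.

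**What to change.** Before the primary analysis is run, name one primary model in SAP 7.3.1.2: Cox regression stratified by site, with treatment, age at dose 1 (continuous), Day-0 slide result (positive/negative) and screening haemoglobin. Then:

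- Judge the success criterion on that model alone. This also settles which fit counts, since the present wording refers to both a stratified and an overall analysis.
- State that its hazard ratio, and so the incremental efficacy, is conditional on the covariates.
- Give a rule that keeps every child in the model when the Day-0 slide is missing or unreadable, for example a separate missing category. Age and haemoglobin are checked for eligibility and should be complete.
- Keep the unadjusted site-stratified Cox model as a sensitivity analysis, so that the marginal hazard ratio is still reported.

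The cost is a paragraph of SAP text and a few lines of code, with no new data. The downsides are the two already named: a conditional rather than marginal primary hazard ratio, and the need for a missing-covariate rule. The trial is open-label, so the covariates and their coding should be fixed before outcomes are examined by group.

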2. OBJECTIVES

2.1. Primary objective

- **Efficacy: Incremental efficacy of a schedule with a fractional third dose at Month 2 over the standard schedule**
 - To demonstrate the superiority of a 3-dose schedule of GSK Biologicals' malaria vaccine RTS,S/AS01_E with a fractional third dose at Month 2 compared to a standard schedule of RTS,S/AS01_E with three full doses in terms of vaccine efficacy against clinical malaria (primary case definition) over 12 months post-Dose 3.

Criterion:

The lower limit of the 95% CI of the incremental vaccine efficacy estimate is above 0.

Refer to Section 11.1 for the definition of the primary endpoint.

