 - When different calendar time follow up periods are compared, as is done for comparison Fx017 versus both Fx012 and R012 during the period 7 and 12 months post dose 3, the following analysis will be performed:
- 1. An analysis comparing the treatment schedules Fx017-20 versus Fx012-14 and R012-14 with respect to clinical malaria and incident infection taking into account potential confounders. The following covariates are considered to be prognostic for clinical malaria: monthly prevalence of parasitemia for control group and study site. An example will be described for comparison Fx017-20 versus both Fx012-14 7 months post dose 3. For the analysis with outcome first or only episode of clinical malaria, a cox regression with outcome time to clinical malaria will be modeled, with treatment as exposure (comparing schedule Fx012-14 from month 2-9 versus Fx017-

20 from month 7-14), monthly prevalence of parasitemia for control group as covariate (continuous) and study site (Ghana versus Kenya). For the analysis with all episodes of clinical malaria, a negative binomial regression (method described in section 7.3.1.2) will be performed. The same exposures and covariates as used for the cox regression will be entered in this model. The adjusted incremental efficacy will be defined as 1 minus the hazard ratio/incidence ratio, during the corresponding time frame for first or only episode/all episodes.

 The estimation of the number of cases of clinical malaria averted will inform on how the vaccine efficacy translates into impact, in a way that is dependent on exposure and hence transmission intensity.

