7.3.1.6. Secondary analyses of efficacy

A) Clinical malaria:

Analysis performed at Month 20:

- Incremental efficacy of Fx012-14 versus (R012-20 + R012-14) over M2.5-M14 (all episodes, PPS).
- Incremental efficacy of Fx012-14 versus (R012-20 + R012-14) over D0-M14 (first or only and all episode, ES).
- Vaccine efficacy of Fx012-14 versus Control group over M2.5-M9 (first or only and all episodes, PPS).
- Vaccine efficacy of Fx017-20 versus Control group over M7.5-M14 (first or only and all episodes, PPS)
- Vaccine efficacy of R012-20 + R012-14 versus Control group over M2.5-M9 (first or only and all episodes, PPS).
- Vaccine efficacy of Fx012-14 versus Control group over M2.5-M14 (first or only and all episodes, PPS).
- Vaccine efficacy of Fx017-20 versus Control group over M7.5-M19 (all episodes, PPS).
- Vaccine efficacy of R012-20 + R012-14 versus Control group over M2.5-M14 (first or only and all episodes, PPS).

- Incremental efficacy of Fx017-20 over M7.5-M14 versus Fx012-14 over M2.5-M9 (first or only and all episodes, PPS).
- Incremental efficacy of Fx017-20 over M7.5-M14 versus groups R012-20 + R012-14 over M2.5-M9 (first or only and all episodes, PPS).
- Incremental efficacy of Fx017-20 over M7.5-M19 versus Fx012-14 over M2.5-M14 (first or only and all episodes, PPS).
- Incremental efficacy of Fx017-20 over M7.5-M19 versus groups R012-20 + R012-14 over M2.5-M14 (first or only and all episodes, PPS).
- Vaccine efficacy and impact of R012-20 + R012-14 versus Control group over D0-M14 (first or only for efficacy and all episodes for efficacy and impact, ES).
- Vaccine efficacy and impact of Fx012-14 versus Control group over D0-M14 (first or only for efficacy and all episodes for efficacy and impact, ES).
- Vaccine efficacy and impact of Fx017-20 versus Control group over D0-M14 (first or only and all episodes, ES).
- Vaccine efficacy and impact of R012-20 versus Control group over D0-M20 (all episodes, ES).
- Vaccine efficacy and impact of R012-14 versus Control group over D0-M20 (all episodes, ES).
- Vaccine efficacy and impact of Fx012-14 versus Control group over D0-M20 (all episodes, ES).
- Vaccine efficacy and impact of Fx017-20 versus Control group over D0-M20 (all episodes, ES).

Analysis performed at Month 32:

- Vaccine efficacy and impact of R012-20 versus Control group over D0-M26 (all episodes, ES).
- Vaccine efficacy and impact of R012-14 versus Control group over D0-M26 (all episodes, ES).

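### If the Month-7 versus Month-2 third-dose all-episodes models are fitted on child-month records, the no-random-effect fallback gives confidence intervals that are too narrow

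*SAP*

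**What the plan says.** SAP 7.3.1.1 covers comparisons whose follow-up windows fall in different calendar periods. It adjusts for study site and for the Control group's monthly parasitemia prevalence as a continuous covariate, first in a Cox model for first or only episodes. For all episodes it refers to the negative binomial method of 7.3.1.2 and adds: "The same exposures and covariates as used for the cox regression will be entered in this model".

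SAP 7.3.1.2 handles repeated episodes in one child through a random effect, from which the overdispersion is estimated. Its contingency rule is: "In case models do not converge or showed poor fit, alternative negative binomial models without random effects will be applied". It names no robust or clustered variance and gives no criterion for non-convergence or poor fit.

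Four all-episodes comparisons are affected (SAP 7.3.1.6 and Table 5): Fx017-20 versus Fx012-14, and Fx017-20 versus R012-20 + R012-14, each over about 6.5 and 11.5 months. One of them reads "Incremental efficacy of Fx017-20 over M7.5-M19 versus groups R012-20 + R012-14 over M2.5-M14 (first or only and all episodes, PPS".

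SAP section 8 calls any lower 95% limit above 0 statistically significant. Its testing hierarchy contains only the primary objective and the 12-month comparison of the Month-7 schedule with three full doses. Everything else is to be read descriptively.

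**The concern.** Whether the fallback is safe depends on how many records each child contributes. With one row per child, the negative binomial dispersion parameter itself describes variation between children, and dropping the random effect does little harm.

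A monthly covariate changes within a child. With child-month rows, the random effect is the only term that ties a child's months together. Without it, the dispersion parameter describes single months, and 7 to 12 correlated records per child are treated as independent.

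The standard error of the schedule contrast is then too small. The intervals for the third-dose-spacing question would be too narrow, and a chance difference could be reported as significant under section 8.

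**Working it through.** **1. The plan's own figure.** The plan states no error rate for the fallback, so the only figure to reproduce is the power in Protocol 11.4 (Determination of sample size). It says "the study has at least 90% power to show a significant incremental vaccine efficacy", with the success criterion "The lower limit of the 95% CI of the incremental vaccine efficacy estimate is above 0", so two-sided alpha is 0.05. Inputs: "assuming 250 evaluable subjects per group and an incidence of at least 0.5 episodes/person year at risk (pyr) in the Control group" and "0.29 episodes/pyr in the standard schedule groups and 0.16 episodes/pyr in the fractional dose schedule", with 500 versus 250 children.

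- Events at 11.5 months: 500(1 − exp(−0.29 × 0.958)) + 250(1 − exp(−0.16 × 0.958)) = 156.9.
- Hazard ratio 0.16/0.29 = 0.552. Schoenfeld: √(156.9 × 1/3 × 2/3) × |ln 0.552| − 1.96 = 1.55, so power is 94.0%.
- With hazard ratio 0.50, power is 98.4%.

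The power claim is reproduced. As an aside, the stated rates imply 44.8% incremental efficacy rather than the stated 50%; the claim holds either way.

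**2. Closed form for the fallback.** Assume gamma frailty between children with variance k, a constant rate, expected count μ = rate × T/12 per child, and T monthly records.

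- True variance of a child's total: μ(1 + kμ).
- Variance implied by independent months: μ(1 + kμ/T).
- Understatement factor: D = (1 + kμ)/(1 + kμ/T).
- Actual two-sided error: 2[1 − Φ(1.96/√D)].

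Example: 0.29/pyr, T = 11.5, k = 1. μ = 0.278 and D = 1.278/1.024 = 1.25, so the error is 7.9%.

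The rates 0.16, 0.29 and 0.5/pyr come from Protocol 11.4. The rate 1.0/pyr and all values of k are assumptions, because the documents give neither an all-episodes rate nor a between-child dispersion.

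| Window (months) | Rate/pyr | k=0.5 | k=1 | k=2 | k=3 |
|---|---|---|---|---|---|
| 6.5 | 0.16 | 5.4% | 5.8% | 6.7% | 7.5% |
| 6.5 | 0.29 | 5.8% | 6.5% | 8.0% | 9.4% |
| 6.5 | 0.5 | 6.3% | 7.6% | 10.0% | 12.3% |
| 6.5 | 1.0 | 7.6% | 10.0% | 14.2% | 17.6% |
| 11.5 | 0.16 | 5.8% | 6.6% | 8.2% | 9.8% |
| 11.5 | 0.29 | 6.5% | 7.9% | 10.8% | 13.4% |
| 11.5 | 0.5 | 7.5% | 10.0% | 14.5% | 18.3% |
| 11.5 | 1.0 | 10.0% | 14.5% | 21.5% | 26.6% |

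**3. Simulation check.** There were 600 trials per scenario (Monte Carlo standard error about 1 point), with no schedule effect, two sites and an assumed seasonal monthly covariate. The fallback was fitted in every run. The table shows 11.5 months, as fallback / same model with child-clustered standard errors.

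| Rate/pyr, k | 250 v 250 | 250 v 500 |
|---|---|---|
| 0.16, 2 | 8.0% / 5.7% | 7.2% / 6.0% |
| 0.29, 1 | 7.3% / 4.3% | 7.7% / 4.3% |
| 0.29, 2 | 12.8% / 6.2% | 13.7% / 6.2% |
| 0.5, 1 | 11.5% / 6.0% | 10.0% / 5.3% |
| 0.5, 2 | 13.8% / 5.0% | 15.7% / 6.3% |
| 1.0, 2 | 20.0% / 3.5% | 22.5% / 5.8% |

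The simulation agrees with the closed form. At the lowest rates and small k, the excess is too small to separate from 5% with this many runs. Over all scenarios, clustered standard errors gave 3.0-7.7%, mostly 4-6%. A child-level negative binomial gave 3.0-7.3%, which confirms that the fallback is harmless with one row per child.

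**The case against.** **The layout is not stated.** Averaging the covariate over each child's window is not excluded. SAP 7.3.1.2 tabulates total events per subject, and the worked example in 7.3.2.1 gives one time at risk per child (277 days). This stands in part: child-month records are an inference. But the 277-day example only computes time at risk and does not fix the regression layout. A window average also sits badly with the covariate's purpose. If prevalence is indexed by study month and pooled over sites, children with full follow-up on one schedule would share the same average, and it would be nearly aliased with schedule.

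**The error is conditional.** It arises only if the mixed model fails or fits poorly, and nothing in the plan says how often that will happen. This stands. The figures above are not the error rate of the planned procedure as a whole.

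**A false-positive rate of 10-20% is a tempting headline, but the documents do not support it.** The comparisons are between vaccine schedules, planned at 0.16 and 0.29/pyr. The 0.5/pyr figure is a floor for Control, and no frailty variance is given.

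**The analyses are mostly not confirmatory.** Section 8 makes at least three of the four descriptive. For the fourth, section 8 does not say whether first-or-only or all episodes is tested. SAP 7.3.2.4 plans a Schoenfeld test for that objective, and 7.3.1.1 prefers first-or-only episodes for the effect of dose spacing; both point to the Cox analysis. A reader might infer that the confirmatory result is at risk, but the documents do not establish that. The primary analysis is a first-or-only comparison by Cox regression and is unaffected.

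**Conclusion.** The point holds conditionally. If the 7.3.1.1 all-episodes models use child-month records and the 7.3.1.2 fallback is triggered, nothing accounts for correlation within a child and the intervals are too narrow.

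For k from 0.5 to 3, the error given use of the fallback is 5.4-9.4% over 6.5 months and 5.8-13.4% over 11.5 months at the planned vaccine-schedule rates. Reaching 10% needs one of the following:

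- over 11.5 months: k of 2 or more at 0.29/pyr, about 1 at 0.5/pyr, or about 0.5 at 1.0/pyr;
- over 6.5 months: about 2 at 0.5/pyr, or about 1 at 1.0/pyr.

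These sizes rest on gamma frailty, an assumed k, and the Protocol 11.4 rates standing in for all-episodes rates. The direction does not depend on the particular values: any positive between-child variance narrows the intervals wrongly. The change is worth making because the stated rule gives wrong error bars whenever a child has more than one record, even for descriptive results.

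**What to change.** In SAP 7.3.1.1, state the record layout (child-month or one row per child) and how the monthly Control prevalence enters the all-episodes model.

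In SAP 7.3.1.2, for any model with more than one record per child, replace the fallback with a log-link Poisson or negative binomial GEE, or a GLM with robust variance, clustered on the child and with a log person-time offset. Keep the negative binomial without random effects only where each child has a single record.

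The cost is a line or two of SAP text, a different model statement in the program, and slightly wider intervals when the fallback is used. In simulation, clustering on the child brought the error back to about 5%.
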